#### 5. TREATMENT PLAN

##### 5.1. IRX5183 Administration:

IRX5183 is an oral capsule that will be administered once daily. Reported adverse events and potential risks are described in Section 9. Appropriate dose modifications are described in Section 6. No investigational or commercial agents or therapies other than those described below may be administered with the intent to treat the patient's malignancy. Patients will be instructed to take the daily dose of IRX5183 each morning after food, as close to the same time as possible. IRX5183 will be self-administered at home, except for days 1 and 14 of cycle 1, on which patients will receive their doses in clinic after trough PK levels are drawn. Each patient will keep a pill diary to help with compliance. If a patient forgets to take a dose in the morning and it is before 8:00 p.m., they should be instructed to take their dose. If the subject forgets to take their daily dose and it is after 8:00 p.m., they should be instructed to wait for the next morning to dose. If vomiting occurs after dosing, the subject should not receive another dose, but instead wait until the next morning to dose.

The schedule of IRX5183 administration and the dose escalation schema are shown in figure 2 and table 1, respectively. At any point, patients will be withdrawn from treatment for undue toxicity, disease progression, and/or deterioration of performance status, per guidelines in section 3.5 above. For **induction therapy**, single agent IRX5183 will be administered orally once daily for two 28-day cycles. Bone marrow assessments will be performed after each cycle, but the primary assessment/endpoint is after cycle 2 of induction. IRX5183 may be held for 5-7 days post induction therapy to allow for study drug wash-out if the PI has concerns that the drug is limiting the interpretation of the assessment marrow testing needed to measure response. All study patients who have drug held only for marrow assessment are eligible to resume study drug following the completion of the marrow testing, while awaiting final pathology review and response assessment.

Patients achieving at least SD, i.e. CR, partial remission (PR), hematologic improvement (HI), or SD,

will be eligible to continue the study treatment planned **consolidation/maintenance therapy**, which will consist of up to four continuous 4 week (28 day) cycles using the same dose of IRX5183 used in the induction phase for each individual patient. This will be referred to as **consolidation** therapy if the patient achieves CR after induction, and will be referred to as **maintenance** if the patient achieves a PR, HI, or SD. Consolidation/maintenance therapy may be initiated following the completion of marrow assessment and no longer than 14 days after completion of induction therapy provided there is no evidence of PD. BM testing will be performed after every other cycle in the consolidation/maintenance phase of therapy. IRX5183 may be held for 5-7 days post each cycle of consolidation/maintenance where a BM assessment will be performed if the PI has concerns that the drug is limiting the interpretation of the assessment marrows. The next cycle of therapy may begin anytime the assessment marrows are completed and no longer than 14 days from the completion of the previous cycle provided there is no clinical evidence of PD.

If the patient is in a CR after 4 cycles of consolidation/maintenance, IRX5183 will be withdrawn and the patient will enter **observation** with biweekly counts for the first month, then monthly for at least 6 months, and bimonthly bone marrow assessments for at least 6 months. If their disease relapses, they will be eligible to re-initiate therapy daily in continuous 4 week cycles.

If the patient achieves at least SD, but not a CR, after 4 cycles of consolidation/maintenance, they will continue on **extended maintenance therapy**, receiving continuous 4-week cycles of daily IRX5183 for up to an additional year. Bone marrow assessments will be required at least every 4 months while the patient is on this extended maintenance phase of therapy. Drug may be held 5-7 days post each cycle of extended maintenance where a BM assessment will be performed if the PI has concerns that the drug is limiting the interpretation of the assessment marrows. The next cycle of therapy will be initiated following the completed marrow testing and no longer than 14 days after completion of the prior cycle provided there is no evidence of PD.

If any patient remains with at least SD after the 1 year of extended maintenance therapy, with no undue toxicity and in good condition, they may be eligible for **extended therapy indefinitely**, per discretion of Io Therapeutics and the Principle Investigator. These patients will continue with bone marrow assessments at least every 6 months and blood counts as clinically indicated.

### **Study Phase I:**

In the dose-escalation part of the study, we will abide by a traditional 3+3 design with 3 dose levels (dose level 1 [DL1] with 50 mg IRX5183, DL2 with 75 mg, and DL3 with 100 mg), with 1 additional dose level, DL(-1), to be only used if excessive toxicity is noted at the DL1. There will be no intra-patient dose escalation.

The first patient will enter the trial on DL1. The dose for level 1 will be a flat dose of 50 mg IRX5183 daily per the schedule above. We will enroll 3 patients at a time to determine the toxicity profile of IRX5183. If none of the 3 patients receiving DL1 experiences a DLT, another 3 patients will be treated at the next higher dose level. However, if 1 of the first 3 patients experiences a DLT, 3 more patients will be treated at the same dose level. The dose escalation will continue until at least 2 patients among a cohort of 3 to 6 patients experiences DLTs. If 2 or more patients experience a DLT on DL1, the next patient will be recruited to DL(-1). The RP2D of single agent IRX5183 will generally be the highest dose at which the DLT rate is <33% in at least six patients. If no MTD is determined, the highest dose

[figure not shown]
explored will be 100 mg. At the end of phase I, the RP2D will be determined after careful review of all of the clinical data available. The first 3 subjects enrolled to any cohort must have passed the 28 day DLT evaluation point before the 4th subject will begin treatment.

IRX5183 will be initiated at the company’s currently recommended dosage for use in APL patients of 50 mg daily (about 30 mg/m^2/day). The drug is available in 25 mg capsules, so we will be using a flat dosage. This dose of 50 mg is above the MTD of 15 mg/m^2/day from the prior phase I trial conducted in solid tumor patients. However, the DLTs seen in this trial were elevations in alkaline phosphatase in patients with known liver metastases. In addition, the phase I/II trial in patients with myeloma and lymphoma used a dose of 60 mg/m^2, which was well tolerated with no serious adverse events (SAEs). The roughly 2 months of induction therapy followed by consolidation/maintenance described above is modeled after prior studies of ATRA and other synthetic retinoids, in which it can take up to 60 days to see an initial response (Lo-Coco et al., 2013; Sanford D, 2014; Tobita et al., 1997).

**Study Phase II:**

The phase II part of the study will use the optimal dose identified in the phase I part of the study and will aim to recruit a total of 27 patients with AML and HR-MDS at the RP2D (see sample size calculation in section 11). The primary goal of the therapy in this phase of the trial is to determine response after receiving at least 2 cycles of therapy per IWG criteria. Analysis of clinical response will take place after the first 13 patients complete induction therapy, and enrollment will continue to the planned 27 patients if the first stage has at least 1 patient achieve a CR or CRi or PR (AML) or CR or PR or HI (MDS). We will halt enrollment after the first 13 patients complete induction therapy until we have their response data. In addition to IWG response, many secondary endpoints will be assessed as outlined in section 11 below.

**Figure 2: IRX5183 Administration Schema.** Induction phase will consist of 56 days of oral IRX5183 daily. Consolidation/maintenance phase will begin once patient has confirmed SD or better and will continue for up to four 28-day cycles. If patient is in CR after consolidation/maintenance, will hold therapy and monitor, and resume therapy if they relapse. If they have SD or better after consolidation/maintenance, they will continue on maintenance therapy for up to 1 additional year. Select patients may be eligible to continue for longer.

**Table 1: Dose Escalation of oral IRX5183 administration in phase I part of the study.** \*: DL(-1) will only recruit if the maximally

administered dose was reached at DL1. DL: dose level.

Dose level (DL)	Daily dose (mg)
DL(-1)*	25
DL1	50
DL2	75
DL3	100

## 5.2. Definition of dose-limiting toxicity:

For purposes of dose-escalation, dose-limiting toxicity (DLT) will be defined as the occurrence of any of the following during the first 28 days of therapy:

- ❖ Any grade 3 or 4 non-hematologic toxicity with the following exceptions:
  - Transient laboratory abnormalities that can be treated or resolve to grade 2 or less within 1 week from holding study drug.
  - Grade 3-4 non-hematologic toxicities that resolve to  $\leq$  Grade 1 within 1 week of holding study drug
  - Grade 3-4 expected and known drug class-related toxicities associated with differentiation syndrome (see definition below in section 9.2.4) that resolve within 2 weeks of steroid therapy to grade 1 will be excluded as DLT for purposes of dose escalation. This is due to the fact that such events are expected of therapy with retinoids that are effectively causing differentiation. If grade 3 or above differentiation syndrome recurs after this time, it will then be considered a DLT.
  - Asymptomatic Grade 3 hypertriglyceridemia will not be considered a DLT for purposes of dose escalation.
- ❖ Grade 4 hematologic toxicity, including only *treatment-associated* aplasia (to be investigated with a BM test) that persists beyond 4 weeks. Given that severe anemia, neutropenia and thrombocytopenia are features of AML and are commonly encountered in this patient population, they will not be used to define DLT except if associated with prolonged treatment-associated aplasia.
  - If the bone marrow at the end of cycle 1 or 2 of therapy is hypoplastic, as defined by less than 5% cellularity, the patient may have a drug-free window of up to 2 weeks to look for count recovery and treatment will be re-initiated after this time if toxicity returns to  $\leq$  Grade 3

Management and dose modifications associated with the above adverse events are outlined in Section 6.

Toxicities will be assessed during the first cycle of therapy and throughout the trial to make sure there are no late adverse effects. If any chronic toxicity becomes apparent, we will evaluate whether changes in trial design are required.

Dose escalation will proceed within each cohort according to the following scheme.

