### 6.1. Dose Modifications for IRX5183:

Decisions to hold or discontinue a specific IRX5183 dose will be made on safety criteria. Treatment with IRX5183 will be skipped or discontinued if the subject experiences at least one adverse event, specified below, considered by the investigator to be “possibly,” “probably,” or “definitely” related to IRX5183 treatment.

Any adverse event that will prompt a skipped dose or discontinuation of IRX5183 must be reported. The investigator should contact the study PI to discuss any questions.

The following criteria will be used to determine dose skipping, restarting doses, or discontinuing IRX5183 during the trial:

It is necessary to avoid study drug dosing and initiate appropriate evaluation and/or treatment for the following adverse events:

Any  $\geq$  grade 3 skin related adverse event regardless of causality.

Any  $\geq$  grade 2 non-skin related adverse event, except for easily correctable laboratory abnormalities that do not reflect underlying organ pathology.

Any  $\geq$  grade 3 laboratory abnormality, aside from cytopenias.

Any adverse event, laboratory abnormality or intercurrent illness that, in the judgment of the investigator, presents a substantial clinical risk to the subject with continued dosing.

It may be necessary to hold study drug to evaluate Grade 1 events that suggest ongoing or incipient differentiation syndrome, including unexplained fever, dyspnea, renal failure, hypotension, and/or unexplained weight gain until diagnosis is determined.

IRX5183 may be restarted if/when the adverse event(s) resolve(s) or returns to baseline or  $\leq$  grade 1 within 2 weeks:

If the adverse event has been determined not to be related to IRX5183: If  $>1$  dose is to be skipped or  $> 1$  week delay is expected due to current events not related to the study, the dosing schedule modifications must be discussed with the principal investigator prior to implementation.

If the adverse event has resolved to  $\leq$  grade 1, IRX5183 dosing may be restarted where the patient left off in their cycle of therapy.

The following criteria will be used to determine dose skipping, restarting doses, or discontinuing IRX5183 during *phase II* of the trial:

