### **11.8.2. Evaluation of response:**

All patients included in the study that complete 2 cycles of therapy will be assessed for response to treatment, even if there are major protocol treatment deviations or if they are ineligible. The primary endpoint to the dose expansion phase is response per IWG criteria after receiving at least 2 cycles of therapy. Only those patients who have measurable disease present at baseline, have received at least 2 cycles of therapy, and have had their disease re-evaluated will be considered evaluable for response. These patients will have their response classified according to the definitions stated in Appendix A. Patients who exhibit objective disease progression prior to the end of cycle 2 will be considered not evaluable and will be taken off study.

An incorrect treatment schedule or drug administration does not result in exclusion from the analysis of the response rate. Patients with disease progression, death due to their disease, and death due to toxicity prior to completion of induction therapy will be excluded from the primary analysis. This will prevent dismissal of an active drug based on progression in patients with highly refractory disease who are unable to receive enough of the drug to see a clinical benefit. Patients who are unable to complete induction therapy for any reason will be treated as missing data and additional patients will be recruited in their place to reach our target sample size of 27 for phase II.

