**Drug relationship:**

The investigator is to classify the study product relationship of an adverse event to the investigational product according to the following definitions. Adverse events that are classified as “possible”, “probable”, or “definite” will be considered drug related.

**1) None:** The time course between the administration of study product and the occurrence or worsening of the adverse event rules out a causal relationship and/or another cause is confirmed and no indication of involvement of the study product in the occurrence/worsening of the adverse event exists.

**2) Unlikely:** The time course between administration of the study product and occurrence or worsening of the adverse event makes a causal relationship unlikely; the known effects of the study product or of the substance class provide no indication of involvement in occurrence/worsening of the adverse event and another cause adequately explaining the adverse event is known; regarding the occurrence/worsening of the adverse event, a plausible causal chain may be deduced from the known effects of the study product or the substance class but another cause is much more probable; or another cause is confirmed and involvement of the study product in the occurrence/worsening of the adverse event is unlikely.

**3) Possible:** Regarding the occurrence/worsening of the adverse event, a plausible causal chain may be deduced from the pharmacological properties of the study product or the substance class, but another cause just as likely to be involved is also known; although the pharmacological properties of the study product or the substance class provide no indication of involvement in the occurrence/worsening of the adverse event, no other cause gives adequate explanation.

**4) Probable:** The pharmacological properties of the study product or of the substance class and/or the course of the adverse event suggest involvement of the study product in the occurrence/worsening of the adverse event, although another cause cannot be ruled out.

**5) Definite:** The pharmacological properties of the study product or of the substance class and the course of the adverse event indicate involvement of the study product in the occurrence/worsening of the adverse event and no indication of other causes exists.

**6) Unclassifiable:** [only used for SAE] The available information is not sufficient for causality assessment.

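### Section 5.2 does not name grade 5 in the non-hematologic DLT criterion, so some toxic deaths would not enter the Table 2 count; it also does not say whether attribution applies

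*Combined protocol and SAP*

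**What the plan says.** Section 5.2 states that "dose-limiting toxicity (DLT) will be defined as the occurrence of any of the following during the first 28 days of therapy". Its non-hematologic criterion is "Any grade 3 or 4 non-hematologic toxicity with the following exceptions". There are four exceptions: transient laboratory abnormalities, events that resolve to grade 1 or less within a week of holding drug, differentiation syndrome that settles on steroids, and asymptomatic grade 3 hypertriglyceridemia. None refers to death, and none removes an event because it is unrelated to the drug.

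The only open-ended grade in section 5.2 concerns differentiation syndrome: "If grade 3 or above differentiation syndrome recurs after this time, it will then be considered a DLT".

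The hematologic criterion is tied to treatment. Of cytopenias it says "they will not be used to define DLT except if associated with prolonged treatment-associated aplasia".

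Section 11.2 refers back to section 5.2 for the DLT definition. Table 2 turns the count into escalation, expansion, the maximally administered dose (MAD), the recommended phase 2 dose (RP2D) or termination.

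Grade 5 and toxic death do appear elsewhere. Section 11.8.2 says that "death due to toxicity prior to completion of induction therapy will be excluded from the primary analysis", and the expedited reporting table in section 7.7 covers grades 3 to 5.

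**The concern.** In a 3+3 design the DLT count is the whole decision rule, and a change of one in a cohort of three changes the action. A definition that stops at grade 4 can leave out the most serious outcome. The protocol expects that such deaths may occur, so the omission cannot be put down to the event being thought impossible. Section 5.1 also says that DL1 lies above the maximum tolerated dose of the earlier solid-tumor trial, so the count at the first level matters.

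The secondary issue is attribution. Patients with advanced leukemia have serious infections and bleeds that the drug did not cause. Section 5.2 does not say whether a persistent event of that kind is a DLT. Two investigators could score the same pneumonia differently, and Table 2 would then give different actions.

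**Working it through.** **The plan's own figure.** Section 11.4 gives up to 18 phase I patients for three dose levels: 3 × 6 = 18, which reproduces. The plan states no operating characteristics for the 3+3 design.

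**Which deaths escape the count.** Taking the text of section 5.2 literally:

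- Death after a grade 3-4 non-hematologic event that never resolved: already a DLT through that event, because the resolution exceptions fail.
- Death from recurrent differentiation syndrome: covered, since that clause has no upper grade.
- Toxic death within 28 days recorded only as grade 5: meets no criterion.

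**Effect on a cohort, for deaths of the third kind and no other DLT (Table 2, below DL3).**

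| Such deaths in 3 patients | Literal score and action | Score and action if counted |
|---|---|---|
| 1 | 0/3, escalate | 1/3, expand to 6 |
| 2 | 0/3, escalate | 2/3, stop |

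**Effect on the chance of escalating.** For a per-patient DLT probability p, a level is passed with 0/3, or with 1/3 followed by 0/3:

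P(escalate) = (1 − p)³ + 3p(1 − p)² × (1 − p)³.

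Two inputs are assumptions, because the documents give neither: other DLTs occur at 10%, and toxic deaths of the third kind occur at rate f.

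- Not counted: p = 0.10, so 0.729 + 0.3 × 0.59049 = 0.906 for every f.
- Counted: p = 1 − (1 − f) × 0.9. For f = 5%, p = 0.145 and P(escalate) = 0.6250 + 0.435 × 0.4569 = 0.824.

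| f | p if counted | P(escalate) if counted | P(escalate) if not counted |
|---|---|---|---|
| 5% | 0.145 | 82.4% | 90.6% |
| 10% | 0.190 | 73.0% | 90.6% |
| 20% | 0.280 | 53.6% | 90.6% |
| 33% | 0.397 | 31.4% | 90.6% |

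**Attribution (secondary).** Suppose the drug causes no DLTs and unrelated events do count. Let q be the 28-day rate of unrelated grade 3-4 non-hematologic events that fail the resolution exceptions. The documents give no q, so a range is shown. Then P(DL1 is the MAD on the way up) = 1 − P(escalate) with p = q. For q = 10% this is 1 − 0.906 = 0.094. The other columns come from exact enumeration of Table 2, including its step-down rules.

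| q | DL1 is the MAD on the way up | DL3 becomes RP2D | Study terminated at DL(-1) |
|---|---|---|---|
| 5% | 2.7% | 91.7% | 0.1% |
| 10% | 9.4% | 72.7% | 1.1% |
| 20% | 29.1% | 32.9% | 10.6% |
| 30% | 50.6% | 10.3% | 31.7% |

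The first column applies equally to DL2 once it is reached. DL3 needs fewer than 2 DLTs in six, so its chance of being the MAD is 1 − [(1 − q)⁶ + 6q(1 − q)⁵], which is 11.4%, 34.5% and 58.0% at q = 10%, 20% and 30%.

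If unrelated events are not counted, an inert drug always reaches DL3.

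**The case against.** **On grade 5.** A reader might infer that the plan ignores toxic deaths altogether. The documents do not support that. Many toxic deaths would pass through an unresolved grade 3-4 event and count that way. The differentiation syndrome paragraph in section 6.1 also treats signs that fail to settle within two weeks of steroids as a DLT. Section 7.7 requires fatal events to be reported at once, section 7.6 lets the trial be put on hold for unexpected and serious toxicity, and section 5.1 has the RP2D set after review of all clinical data. In practice a toxic death would probably not be overlooked. This narrows the gap but does not close it: the hold is limited to unexpected events, the data review comes at the end of phase I, and neither changes the number entered in Table 2.

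**On attribution.** A reader might also infer that section 5.2 counts every event whatever its cause. It does not say so; it is silent, and usage points both ways.

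- For a drug-related reading: section 11.2 speaks of the toxicity of IRX5183, and section 11.8.2 separates deaths from disease from deaths from toxicity. Section 6.1 ties dose holds to possible, probable or definite relatedness, yet writes "skin related adverse event regardless of causality" where it means cause not to matter.
- Against it: section 6.2 applies the word toxicity to motor neurologic events irrespective of cause, beside sensory events that must be treatment related. Neither qualifier would be needed if the word already implied cause.
- Section 12.1 requires a causality rating ("The investigator is to classify the study product relationship of an adverse event to the investigational product according to the following definitions"), but nothing links it to the DLT count.

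Counting events without relying on investigator attribution is also a defensible choice in a small open-label cohort. The rate q excludes events that resolve within a week of holding drug, and section 3.2 excludes some patients with active infection. Nothing in the documents supports the upper end of the range. These arguments stand, so this part is a request for clarification and not a finding of error.

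**Conclusion.** The grade 5 point holds. Section 5.2 is the only DLT definition and its non-hematologic criterion stops at grade 4. A toxic death in the window with no earlier unresolved grade 3-4 event, and outside the differentiation syndrome clauses, therefore scores zero. The result is wrong by one DLT per such death, enough to turn expand or stop into escalate in a cohort of three. How often this would happen is unknown. The probabilities above rest on assumed rates for such deaths and for other DLTs, and they show sensitivity only. No stated figure in the plan is wrong.

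The attribution point holds only as an omission: the plan does not state which reading applies. The consequence depends on an assumed rate, from small at 5% (2.7% stop at DL1 with an inert drug) to large at 30% (50.6%).

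**What to change.** - **Section 5.2, non-hematologic criterion:** add grade 5 so that the DLT count covers grade 5 toxicity as well as grades 3 and 4. Leave the existing exceptions applying to grades 3-4 only, unchanged. This costs a short phrase in an amendment and no new data, since deaths are already reported. Any cohort already scored should be re-read against the amended text.
- **Attribution, clarification only:** state in section 5.2 whether the relationship to drug matters for non-hematologic events, including deaths, and reconcile this with the hematologic criterion and with sections 6.1, 6.2, 11.8.2 and 12.1. Which reading applies is for the sponsor to decide. The ratings are already collected under section 12.1, so either choice costs a sentence. Whichever is chosen, it should be written down before cohorts are scored.
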